College of Medicine
Department of Pediatrics
Division of Neonatology
Health Science Center

[name]
[name]
[name]
Office: [contact]
[contact]

Title: Research on current prototypes of the Digiclamp. Short term and long term outcomes of treating adults with achrocordons (skin tags)

NCT Number: 03259295

Date of Document: July 17, 2017

Protocol

Project Title:

"Research on current prototypes of the Digiclamp. Short term and long term outcomes of treating adults with achrocordons (Skin tags)"

Investigators:

[name]
[name]
[name], NNP
[name], NNP

Abstract:

[figure not shown]
[name] and XDG Technologies LLC have developed a proprietary, hand-held medical device (the "Digiclamp" or "device") for the treatment of both a genetic medical condition called polydactyly (i.e. extra fingers or toes) and the removal of skin tags. The current standard of care for both conditions requires a thin thread (i.e. a "suture") to be tied very tightly at the base of the extra finger/toe or the skin tag, restricting blood flow and causing the tissue to subsequently blacken and "die" (necrose) over a period of 7-14 days, then fall off. For the purpose of this study in particular we propose instead that the Digiclamp can be used to change the current standard of care for these conditions (and others) by resolving them in 10 MINUTES. This proposed project will help validate the short-term and long-term clinical efficacy of the Digiclamp specifically for treating adults who are affected by achrocordons. The use of the Digiclamp device to treat adults who suffer from this condition will demonstrate its clinical superiority over the currently accepted "standard of care" - and may lead to the clamp becoming the most common method in the U.S. The clamp procedure is the more comfortable, less costly, and more desirable option for these patients.

The patients who undergo removal of the achrocordons, will subsequently be followed after the removal at 3-6 months to determine if any recurrence, scarring, or discoloration of the skin has occurred. At that time, the patients will be asked to answer a simple survey of satisfaction to determine their opinion of the method used. Pictures of the skin tags before and after its removal will be obtained, in order to demonstrate the resolution of the lesion, or to document any secondary finding that may have taken place. Since discoloration, and scarring are complications associated with the other methods used to remove skin tags such as suture ligature, cryotherapy or cautery documentation of how these lesions progress after their removal with the Digiclamp is essential.

Background:

Achrocordons or skin tags are superficial cutaneous lesions (ICD 10: Skin tags L91.8; Congenital: Q82.8). These skin growths are generally clinically benign and occur most frequently in middle age adults who are 45 years of age or older. Generally, achrocordons are non cancerous, and characteristically protrude from normal underlying skin in the neck, axillae, groin or skin folds attached by a narrow "stalk like" pedicle. Histologically skin tags are made up of loosely arranged collagen fibers and blood vessels surrounded by a thickened thinned out epidermic layer as its cover. They affect men and women similarly, and cosmetically appear darker in color than the underlying normal skin in the area. Obese persons and those who suffer Type 2 diabetes are affected by these growths more frequently than other persons.

Appearance of typical achrocordon or skin tag:

© [name]. Used by DermNet New Zealand with permission.

In most cases it is not necessary to treat or to remove skin tags, and usually these lesions are not bothersome. The person affected by these lesions most often would choose to remove them for cosmetic reasons if a reasonably priced, safe and effective option was available. There are instances when these growths become infected or irritated due to friction and can change in appearance, and may swell, bleed or become infected and their removal may become necessary. In these situations, as in the elective cases, there are several treatment options available to the patient. The patient may undergo suture ligature by tying a band, or a suture string at the base of the skin tag and choking off the circulation to the lesion. The patient may opt to freeze the lesions with a refrigerant such as Liquid Nitrogen or Nitrous Oxide. The lesion can also be burned off by means of an electro cautery device. Finally, the lesion can be excised using scissors or scalpel. There are no topical creams currently recommended as a medical option to remove achrocordons. The use of a topical anesthetic prior to the removal of these lesions is recommended for most of the options mentioned, however anesthesia isn't necessary. Usually, the procedure is performed by a Dermatologist in an office. Most insurance companies designate the removal of skin tags as a cosmetic procedure therefore, in most instances, their removal represents an "out of pocket" cost to the patient.

Approximately 50% of adults over the age of 45 are affected by one or more of these lesions, thereafter the risk increases with the patient's age. In most instances, a person has multiple lesions and if they desire the lesion(s) removed, the cost of removal can range anywhere from \$100 to \$300 per intervention.

depending on what method is used. Currently, there is a great need for an effective and inexpensive disposable device to remove these lesions that can be readily accessible to the primary care clinicians to use in their office. At this time, clinicians have had to rely on ligature which takes 7-14 days to resolve if successful; cryotherapy which requires expensive equipment, may be painful, and may leave an area of discoloration after the removal; cautery which is associated with pain, blistering, scarring, and also requires special equipment. Because of these associated complications, and the costs to the primary physician, they very frequently refer the patient to a sub-specialist such as a Dermatologist for this procedure. The primary caregivers have not had a reliable and inexpensive tool for removing and resolving these lesions. The Digiclamp represents a new option that when placed in the hands of these clinicians, will allow them to retain this very substantial group of patients, and to treat them without having to purchase expensive devices or to refer them to a Dermatologist. The study we are hoping to conduct will demonstrate that the Digiclamp is easy to use, quick and definitive in the removal of such lesions with less complications associated. The device is disposable, and relatively painless when used correctly, and requires minimal training. There is no need for cautery, suturing of any sort associated with the use of the Digiclamp. The procedure takes approximately 10 minutes to complete. As such, we feel that the Digiclamp is a very logical step in the management of patients with skin tags. Most importantly, in cases where the lesion requires a biopsy excision for pathologic evaluation, the Digiclamp represents a very logical option since cautery or cryotherapy may be precluded due to the effect on the tissue being removed for analysis.

VIEWS OF DIGICLAMP

Specific Aims:

The objective of the study is to treat adults with skin tags or achrocordons who wish to have these lesions removed permanently, using the Digiclamp. After removal of their lesion, these patients will be reassessed after a period of no less than 3 months and, during that visit, pictorial documentation of the lesion site will be collected to demonstrate the effectiveness of the Digiclamp in removing the lesion. The patients will then be asked to complete of a questionnaire of their satisfaction.

Our aim is to demonstrate that the lesions removed using the Digiclamp will be resolved permanently. Also, that the site of the lesion will demonstrate minimal or no scarring, discoloration, recurrence or discomfort.

Research Plan:

We propose to enroll 25 adult patients with achrocordons to the study. These patients will have their skin tags removed by using the Digiclamp. The diagnosis the achrocordons will take place on the initial visit, and will be based on their clinical appearance of being an outgrowth of normal appearing skin attached to the underlying area by a narrow stalk. The initial visit of the study will also include photographing the lesion as well as measuring the dimensions of the skin tag (height, width).

The patients will also be asked if they have any allergy to topical anesthetic prior to removal of the skin tag. The area of the skin tag will be photographed and measured. The skin tag as well as the skin in the immediate area will then be cleaned and prepped in a sterile fashion using Chlorhexidine solution or Betadyne plus alcohol and a topical anesthetic such as Lidocaine 1% solution will be used subcutaneously or a topical cream such as Emla placed on the skin tag. The Digiclamp will then be fitted over the lesion and clamped and held in place until the lesions blanches. After 3-5 minutes, the lesion will be excised using a scalpel (#15 blade) and the clamp will be removed showing a translucent skin flap present at the base of where the skin tag had been. The area will then be covered using a small band aid, and the patient will be instructed to keep the band aid on until it naturally falls off. The patients will be asked to report any presence of post procedure bleeding, erythema, edema to the clinical coordinator after the removal.

The patients will be re-evaluated after a period of approximately 3 months for the presence of any secondary effects such as reoccurrence of the lesion, presence of scar tissue at the removal site, discoloration of the area, hyper-pigmentation, and hyper- or hypo- sensitivity.

The inclusion criteria will be adults over the age of 18 years of age with simple achrocordons up to 1 centimeter width at the base. The exclusion criteria will include minors (less than 18 years of age), patients with lesions that are too large for adequate removal (> 1 cm at the base), whose lesions appear infected, or that are located in the genital areas or the eyelids. Also excluded are patients that have lesions that are not achrocordons and or may need their lesions evaluated by pathology, and patients with bleeding disorders.

Possible Discomforts and risks:

The potential risks in this study are minimal, but could include: (1) allergic reaction to Chlorhexidine or Betadyne solution, (2) reaction to the local anesthetic, (3) pain when compressing the base of the skin tag, (4) bleeding from the site after removal of the skin tag, (5) site infection after removal. However, during this study we will observe safeguards to mitigate potential risks. The mitigation of the risks will occur by: (1) using either Chlorhexidine or Betadyne if the patient is sensitive to either solution. (2) reaction to local anesthetic or diminution of pain will be reduced by using topical anesthetic or no anesthetic in patients whom may be sensitive to "-caine" anesthetics or have Methemoglobinemia. (3) bleeding post removal will be mitigated by excluding patients with a bleeding diathesis. (4) risk for infection at the removal site will be decreased by observing strict sterile procedure for the removal also, a sterile disposable clamp will be used for each individual procedure.

Possible Benefits:

The direct benefits to the patients will be mainly esthetic in nature. The patient will have the lesion rapidly and permanently removed when using this procedure. This procedure does not require stitch removal as would be required if excised with scalpel, without the risk of burning, or blistering as can occur with the cautery or freezing these lesions. In situations where a clinical indication to remove the skin tag exist, as is the case when these lesions become inflamed due to friction with clothing or with jewelry, the Digiclamp procedure represents an effective, less costly option readily available for use by the Primary Care personnel precluding the need for referral to a specialist. Commercially, the Digiclamp represents a new standard of care in the removal of benign skin lesions, easy to use, disposable, and inexpensive.

Conflict of Interest:

The Digiclamp (TM) is a patent pending, FDA Class 1 device which was invented by [name] who is currently an Associate Professor at University of Florida, Department of Pediatrics, Division of Neonatology. [name] and the University of Florida wish to disclose that they stand to profit from the Commercialization of the device.

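### The Abstract and Background promise superiority and fewer complications, but all 25 patients receive the Digiclamp and the protocol gives nothing to compare them with

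*Protocol*

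**What the plan says.** Two sentences in the protocol state comparative conclusions as something the study will show.

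- **Abstract.** Use of the device in adults with skin tags "will demonstrate its clinical superiority over the currently accepted" standard of care. Earlier in the same paragraph that standard is described as tying a suture at the base of the lesion, which then falls off after 7-14 days. The Digiclamp is said to change this standard "by resolving them in 10 MINUTES".
- **Background.** The study is expected to show that the device is easy to use, quick and "definitive in the removal of such lesions with less complications associated". The same paragraph has just listed the drawbacks of the alternatives: the time ligature takes, cryotherapy which "may leave an area of discoloration after the removal; cautery which is associated with pain, blistering, scarring".

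The Research Plan sets out the design in these words: "We propose to enroll 25 adult patients with achrocordons to the study. These patients will have their skin tags removed by using the Digiclamp". Patients report bleeding, redness or swelling after the procedure to the coordinator. Then, "The patients will be re-evaluated after a period of approximately 3 months for the presence of any secondary effects": recurrence, scar tissue, colour change and altered sensitivity. The Abstract adds photographs and says that "the patients will be asked to answer a simple survey of satisfaction to determine their opinion of the method used".

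Two other places are non-comparative. The Abstract explains the follow-up by saying that "documentation of how these lesions progress after their removal with the Digiclamp is essential". The Specific Aims speak only of permanent removal with little or no scarring, discoloration, recurrence or discomfort.

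**The concern.** Superiority, and fewer complications, are each statements about two quantities. The study produces one of them. A report that followed the Abstract and Background would state a conclusion that its data do not contain, however well the 25 patients fared. Favourable Digiclamp results could be read as showing that it does better than ligature, cryotherapy or cautery, when no patient in the study received any of those and no rate for them is given.

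**Working it through.** The protocol states no hypothesis, effect size or comparator rate, so there is no figure of its own to reproduce. The check is whether each term of the promised comparisons can be obtained from the plan.

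**1. What the claims need.** Write p_D for the proportion of Digiclamp patients with a given complication and p_C for the same proportion with a comparator method. The Background claim is p_D − p_C < 0. The Abstract claim needs the same kind of contrast on whatever clinical outcome is meant by superiority.

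**2. What supplies p_D.** The Research Plan: 25 patients, all treated with the Digiclamp.

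**3. What could supply p_C.**

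| Possible source | What the protocol gives |
|---|---|
| Concurrent control group | None; 25 − 25 = 0 patients receive another method |
| Control lesion within the same patient | None described |
| Historical series or performance goal | None described |
| Complication rate for ligature, cryotherapy or cautery | None; complications are named in words only (Abstract, Background) |
| Time for ligature | 7-14 days (Abstract, Background) |
| Price of removal | $100 to $300 per intervention (Background) |

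The two comparator figures that exist are a time and a price. Neither is a complication rate, so p_C has no value and p_D − p_C cannot be computed.

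**4. Whether the data collected help.** Patient-reported bleeding, erythema and edema; recurrence, scarring, discoloration and sensitivity at follow-up; photographs; satisfaction. All of these are observed after Digiclamp removal only. The satisfaction survey asks about the one method the patient had in this study.

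**5. Whether sample size matters.** It does not. With n Digiclamp patients and no comparator, p_D becomes more precise as n grows and p_C stays unknown. At n = 2,500 the comparison would be just as absent as at n = 25.

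**6. The time contrast.** For time the protocol does set two figures against each other: 7-14 days and 10 minutes. They can be placed side by side, but no ligature patient is treated, so the result is a descriptive contrast. It says nothing about complications.

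**The case against.** The strongest reply is that both sentences are rationale. They sit in the Abstract and Background, the sentence before the superiority claim speaks only of helping to validate efficacy, and the Specific Aims, which govern the study, make no comparison. No comparative test is planned, so harm arises only if a later report follows the introductory prose. This stands as a limit on weight: the descriptive study is sound on this point. It does not remove the mismatch, because both sentences say what will be demonstrated and the aims and design do not deliver it.

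A second reply is that superiority means speed. The Abstract permits that reading, and the difference in time follows largely from the procedures themselves: necrosis over days against excision after a few minutes of clamping. This stands for time, as a descriptive contrast. It cannot carry the Background's claim about complications.

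A third is that an analysis plan, not shown here, could name an external benchmark. That is possible, and the absence noted here is only from the protocol. But no analysis plan can add a concurrent group to a single-arm enrolment plan.

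A fourth is that the Background phrase names no comparator. True, but it closes a paragraph on the faults of ligature, cryotherapy and cautery, and fewer has no meaning without something to be fewer than. It is the less explicit of the two claims.

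**Conclusion.** The point holds as a conflict between stated conclusions and design. Two sentences promise comparative conclusions; 0 of 25 patients receive a comparator; complication rates are stated for 0 of the 3 methods with which the Background contrasts the device. This rests on the protocol text alone and on reading the Background phrase in its paragraph. It should be corrected before results are reported.

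A reader might infer more than the document supports:

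- **That the study needs a control arm.** It does not for its Specific Aims, which a single-arm series can serve descriptively. A comparator would be needed only to keep the comparative claims.
- **That 25 patients are too few, and that this is the defect.** The gap is structural. Precision or power figures would not measure it, and any power figure would rest on comparator rates that the protocol does not give.
- **That the remarks on comfort, cost and desirability (Abstract, Possible Benefits) are failed promises of the same kind.** They are the investigators' opinions, not results that the study says it will show.
- **That the wording on permanent removal falls under this point.** Whether the length of follow-up can support permanence is a separate question and is not decided here.

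**What to change.** **Abstract.** Replace the superiority claim with, for example: *The study will describe the short-term and follow-up results of the Digiclamp in this series of adults with skin tags.* If 7-14 days is set against 10 minutes, label it a descriptive contrast on time.

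**Background.** Replace only the phrase on fewer complications with, for example: *The study will estimate the proportions of patients with recurrence, scarring, discoloration, altered sensitivity, and post-procedure bleeding, erythema or edema. It will draw no conclusion of superiority over other methods or of fewer complications than with them.*

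The Specific Aims and the Research Plan need no change on this point.

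**Cost.** One sentence and part of another are reworded. No patients, visits or data are added. The downside is that the protocol states a more modest ambition for the device.

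### The aim of permanent resolution, and the promise of long-term outcomes, go beyond the one planned follow-up visit, which need not be later than about 3 months and is timed in three different ways

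*Protocol*

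**What the plan says.** **The claim.** The title announces "Short term and long term outcomes of treating adults with achrocordons", and the Abstract says the project will "help validate the short-term and long-term clinical efficacy of the Digiclamp". Specific Aims goes further: "Our aim is to demonstrate that the lesions removed using the Digiclamp will be resolved permanently". Its next sentence adds that "the site of the lesion will demonstrate minimal or no scarring, discoloration, recurrence or discomfort". Possible Benefits tells the reader, as a fact and not as a hypothesis, that removal is permanent. Neither permanence nor long term is defined anywhere.

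**The follow-up.** The Abstract, Specific Aims and Research Plan each describe a single reassessment, and each times it differently:

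- Abstract: patients are "followed after the removal at 3-6 months to determine if any recurrence, scarring, or discoloration of the skin has occurred".
- Specific Aims: patients are "reassessed after a period of no less than 3 months".
- Research Plan: "The patients will be re-evaluated after a period of approximately 3 months".

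The only other contact after the procedure is in the Research Plan: "The patients will be asked to report any presence of post procedure bleeding, erythema, edema to the clinical coordinator after the removal". That list covers acute effects and does not include recurrence.

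**The concern.** A statement that a lesion has gone for good is a statement about all later time. The protocol looks once, at a time that may be as early as about 3 months, and then stops. If the study is run and reported as written, a clean result at that visit could be presented as having met an aim that the data cannot address. Possible Benefits already states the conclusion, and the protocol discloses that the inventor and the university stand to profit from the device. Both are reasons to keep the claim within the evidence.

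The three timings add a second difficulty. A recurrence proportion means little without the time to which it refers, and here that time is not fixed. Staff scheduling a visit slightly before 3 months, or after 6 months, would find one section that permits it and another that does not.

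**Working it through.** The protocol gives no figure on this point to reproduce: no recurrence rate, time course, error rate or power. The check is therefore a comparison of passages plus a count of follow-up time.

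**Step 1. What each section allows.**

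| Visit at | Abstract (3 to 6 months) | Specific Aims (at least 3 months) | Research Plan (about 3 months) |
|---|---|---|---|
| Slightly before 3 months | not allowed | not allowed | allowed |
| 3 months or just after | allowed | allowed | allowed |
| 6 months | allowed | allowed | hard to call approximate |
| After 6 months | not allowed | allowed | not allowed on a plain reading |

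The three wordings overlap at or just after 3 months, so they are not mutually exclusive. They disagree at the edges. A patient seen once at 3 months satisfies all three, so nothing obliges later observation.

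**Step 2. Follow-up time for recurrence.** Inputs: 25 patients (Research Plan), and 3 and 6 months (Abstract; 3 months also in Specific Aims and the Research Plan). Assumption: all 25 attend. The count is per patient because the visit is per patient.

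- Everyone seen at 3 months: 25 × 3 = 75 patient-months. This is approximate as a minimum, since the Research Plan tolerates slightly earlier visits.
- Everyone seen at 6 months: 25 × 6 = 150 patient-months. Specific Aims sets no upper limit.
- Ratio of latest to earliest visit in the Abstract's own window: 6/3 = 2.
- Scheduled after the visit, under any wording: 25 × 0 = 0 patient-months.

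**Step 3. How much one visit might miss (illustration only).** Suppose that, among lesions that would ever recur, time to recurrence is exponential with median *m* months. The share that has recurred by month *t* is 1 − 0.5^(*t*/*m*). The values of *m* are assumptions, chosen to show a range:

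| Assumed median *m* (months) | Share by 3 months | Share by 6 months |
|---|---|---|
| 3 | 1 − 0.5^1 = 50% | 1 − 0.5^2 = 75% |
| 6 | 1 − 0.5^0.5 = 29% | 1 − 0.5^1 = 50% |
| 12 | 1 − 0.5^0.25 = 16% | 1 − 0.5^0.5 = 29% |
| 24 | 1 − 0.5^0.125 = 8% | 1 − 0.5^0.25 = 16% |

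If instead every recurrence appears before 3 months, a visit at 3 months or later misses nothing. The protocol does not say where in this range the truth lies.

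**Step 4. The best possible result.** With no recurrences in 25 patients at the visit, the exact one-sided 95% upper limit for the proportion of patients with recurrence by that visit is 1 − 0.05^(1/25) = 11.3%. That limit refers to the visit and carries no information about later recurrence.

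**The case against.** The strongest reply is that this is loose drafting and not a design fault. On timing, the Abstract gives a range, Specific Aims gives its floor, and the Research Plan gives a rough target; any visit from 3 to 6 months satisfies the first two. On the label, long term can be read as the later of two layers: acute effects reported by the patient, then the follow-up visit. Recurrence is a named outcome, so permanence has at least a partial operational meaning. The patient-month counts only restate the window, and no changed conclusion has been shown.

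Much of this stands. The timing conflict is confined to the edges and alone would be a minor harmonisation. Calling the later visit long term is arguable, because the protocol has no time course against which to judge it. No outcome is missing. The effect on the recurrence result is unknown and may be nil.

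The reply does not rescue the aim. Permanence is the substance of the stated aim and reappears in Possible Benefits. Reading long term as the follow-up visit leaves that claim where it was, and a visit at 6 months would not establish it either. Nor can a statistical analysis plan repair it, since such a plan cannot supply observation that was never scheduled.

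**Conclusion.** The point holds, and the aim is wrong as written. The protocol sets out to demonstrate permanent resolution, but its design can show only absence of recurrence at the treated site at one visit, which need not be later than about 3 months. Follow-up per patient may differ two-fold within the Abstract's own window, and scheduled observation for recurrence after the visit is nil. These figures rest on the protocol's 25 patients and its stated visit times; the patient-month totals also assume full attendance. The exponential illustration rests on assumed medians, and the conclusion does not depend on it. The matter bears on the headline conclusion, not on patient safety or feasibility, and should be corrected.

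**What to change.** 1. In Specific Aims, restate the aim as no recurrence at the treated site at the follow-up visit, with results reported alongside actual follow-up times.
2. In the title and Abstract, align the long-term wording with the follow-up actually planned, or define the term as that visit. In Possible Benefits, remove the assertion of permanence.
3. In the Abstract, Specific Aims and Research Plan, state one visit window with a lower and an upper bound, worded identically. The Abstract's window is the only one that already has both bounds.

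The cost is wording in these places and a less favourable claim; no visit is added and no patient is excluded. If the sponsor wishes to claim outcomes beyond this visit, a later assessment of recurrence would have to be scheduled. That is a larger change, and it would support a claim only up to the time of that assessment.

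### Between the end of the procedure and the follow-up visit, complications are captured only by asking patients to report them, so short-lived events may be under-counted

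*Protocol*

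**What the plan says.** The Research Plan describes the procedure up to the dressing and then gives the one early safety instruction: "The patients will be asked to report any presence of post procedure bleeding, erythema, edema to the clinical coordinator after the removal". All patients are asked, and the recipient is named. No day, window, telephone call, diary or early visit is attached to the request.

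The next stated contact with every patient is the follow-up visit. Its timing is worded in three ways:

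- Abstract: patients "will subsequently be followed after the removal at 3-6 months to determine if any recurrence, scarring, or discoloration of the skin has occurred".
- Specific Aims: "these patients will be reassessed after a period of no less than 3 months".
- Research Plan: patients are "re-evaluated after a period of approximately 3 months for the presence of any secondary effects such as reoccurrence of the lesion". The list then continues with "presence of scar tissue at the removal site, discoloration of the area, hyper-pigmentation, and hyper- or hypo- sensitivity".

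The Abstract adds photographs before and after removal, partly "to document any secondary finding that may have taken place". It and the Specific Aims also place a satisfaction questionnaire at this visit.

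Under Possible Discomforts and risks, two of the numbered risks arise after the lesion is off: "4) bleeding from the site after removal of the skin tag, (5) site infection after removal". The last sentence of the Specific Aims says that "the site of the lesion will demonstrate minimal or no scarring, discoloration, recurrence or discomfort".

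**The concern.** A report that depends on the patient gives information in one direction only. A report means an event. The absence of a report may mean no event, or an event that the patient thought too small to mention, forgot, or did not recognise as reportable. Nothing in the protocol separates these cases, because no recorded answer of no is obtained from anyone.

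The follow-up visit does not reliably close the gap. The effects named for it are findings present on the day. A bleed or a site infection that settled weeks earlier need leave nothing to see or photograph, and no question about the interval is stated.

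If reports are true but incomplete, the error runs one way, toward fewer complications with the device. The title names short-term outcomes, and the Background expects the study to show fewer complications. A later analysis plan can choose how to count what was recorded, but it cannot recover answers that were never collected.

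**Working it through.** The protocol gives no early event rate, no reporting rate and no derivation of the 25 patients, so there is no figure to reproduce. The check has two parts.

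**1. Each event against the places where it could be captured after the procedure**

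| Event | Where the protocol raises it | In the patient report list? | Named for the follow-up visit? |
|---|---|---|---|
| Bleeding | Risk 4 | Yes | No |
| Site infection | Risk 5 | No (erythema and edema overlap in part) | No (the list is open-ended) |
| Erythema, edema | Report list | Yes | No |
| Discomfort at the site | Specific Aims | No | Only altered sensitivity comes near it |
| Scarring, discoloration, recurrence | Specific Aims, Abstract | Not needed | Yes |

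The first three rows depend mainly on the patient coming forward. The last row is assessed in every patient at the visit and is unaffected. The gap is the same under each of the three visit timings, since the earliest is about 3 months.

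**2. What a missed patient is worth**

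Input from the Research Plan: n = 25, one group, all treated with the device. Everything else here is assumed and serves as illustration.

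- One patient with an unrecorded event lowers the observed proportion by 1/25 = 4.0 percentage points.
- One-sided 95% exact (Clopper-Pearson) upper limit for x events: BetaInv(0.95; x + 1, 25 − x).
  - x = 0: 1 − 0.05^(1/25) = 11.3%.
  - x = 1 (4.0% observed): 17.6%.
  - x = 2 (8.0% observed): 23.1%.
- So a recorded 0 of 25 that hides one or two affected patients would show 11.3% where 17.6% or 23.1% belonged.
- Let s be the assumed share of affected patients who report, with independent patients and no false reports. After 0 of 25 recorded, the limit on the true risk is 11.29%/s: 14.1% at s = 0.8 and 22.6% at s = 0.5.
- Let p be the assumed true risk. The chance that no event at all is recorded is (1 − p·s)^25:

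| p | s = 1 | s = 0.8 | s = 0.5 | s = 0.3 |
|---|---|---|---|---|
| 5% | 27.7% | 36.0% | 53.1% | 68.5% |
| 10% | 7.2% | 12.4% | 27.7% | 46.7% |
| 20% | 0.4% | 1.3% | 7.2% | 21.3% |

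For p = 10% and s = 0.5, for example, (1 − 0.05)^25 = 27.7%, against 0.90^25 = 7.2% with full reporting. The expected number of patients with a recorded event falls from 25 × 0.10 = 2.5 to 1.25.

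**The case against.** The strongest reply is that the protocol's emphasis lies elsewhere. The Abstract names discoloration and scarring as the complications that make documentation essential, and both are examined at follow-up. The short-term claim developed there is resolution within minutes, which the operator sees. Bleeding, erythema and edema are in no stated aim, and the risks are described as minimal. This stands in large part. A reader might infer that the study promises an early complication rate, or that the expectation of fewer complications rests on early events. The documents support neither: no such rate is promised, and that expectation points mainly to follow-up findings.

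A reader might also infer that all early complications depend on self-report. They do not. Pain on compression, immediate bleeding and most reactions to the antiseptic or anesthetic would arise with staff present. The gap opens only when the procedure ends.

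The discomfort aim is best read as discomfort at the follow-up visit, beside the other three site findings. Altered sensitivity is assessed there, and the satisfaction questionnaire, whose content is not shown, may touch on it. Discomfort is therefore weak evidence for the gap.

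Erythema and edema are visible signs of infection, and the follow-up list is open-ended, so the infection gap is partial. The protocol does not say whether the coordinator waits for reports or seeks them, and consent pages and case report forms, which are not at hand, could hold more. That is possible but not established.

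None of this supplies a dated contact or a recorded no. An unseen analysis plan cannot supply one either.

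**Conclusion.** The point holds in a limited form and should be corrected before enrolment. From the end of the procedure to the follow-up visit, the stated capture method can under-count short-lived events, and any such error favours the device. Site infection, a risk that the protocol itself names, is explicitly in neither list and is only partly covered.

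The size of the under-count is unknown and cannot be derived from the documents. The only figure that follows from the protocol alone is 4.0 percentage points per missed patient. The upper limits and probabilities above rest on hypothetical missed events or on assumed risks and reporting shares; they show sensitivity and are not evidence that events will be missed.

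It would be too strong to conclude that the study's main findings are undermined. Scarring, discoloration and recurrence at follow-up, and events during the procedure, are unaffected.

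**What to change.** Keep the Research Plan's request that patients report, and add the following.

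- **At the existing follow-up visit:** ask every patient a fixed yes/no question on each of bleeding, erythema, edema, signs of site infection and discomfort, covering the whole period since removal, with an approximate date for each yes. This alone separates no event from not reported, subject to recall.
- **Early contact:** because recall over 3 months or more is weak, the coordinator already named makes one brief contact with every patient using the same checklist, in a window that the investigators fix before enrolment.
- **Counting rule:** a patient has an event if it is recorded by any route (self-report, contact or visit). A patient is event-free only if the checklist was answered at least once and no event was recorded by any route.
- **Denominator:** all patients with an event recorded or a checklist answered, so that someone who self-reports and is later not reached stays in both numerator and denominator. With E patients having an event, F event-free and U with no information, report E/(E + F), state U separately, and show (E + U)/25 with the unknowns counted as events.

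The cost is about 25 short contacts and five yes/no items at a visit already planned. The recorded complication rate may look less favourable. The change concerns data collection and counting, and leaves clinical management as it is.
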